10.6. Abbreviations and Definitions

Abbreviation	Definition
ADA	anti-drug antibody
AE	adverse event
ALT	alanine aminotransferase
AN	abscess and inflammatory nodule
AST	aspartate aminotransferase
AUC₀-∞	area under the plasma concentration-time curve from time zero to infinity
$\mathrm{AUC}_{0 ext{-} au}$	area under the plasma concentration-time curve over a dosing interval
BID	twice daily
CI	confidence interval
CFR	Code of Federal Regulations
C_{max}	maximum plasma concentration
COVID-19	coronavirus disease of 2019
CRF	case report form
CRO	contract research organization
C-SSRS	Columbia-Suicide Severity Rating Scale
CV%	percent coefficient of variation
DLQI	Dermatology Life Quality Index
DMC	Data Monitoring Committee
ECG	electrocardiogram
EQ-5D	European Quality of Life-5 Dimensions
EudraCT	European Union Drug Regulating Authorities Clinical Trials
FAS	Full Analysis Set
FSH	follicle-stimulating hormone
GCP	Good Clinical Practice
HADS	Hospital Anxiety and Depression scale
HBV	hepatitis B virus
HBcAb	hepatitis B core antibodies
HBsAb	hepatitis B surface antibodies
HbsAg	hepatitis B surface antigen

Abbreviation	Definition
HiSCR	hidradenitis suppurativa clinical response defined as at least a 50% reduction from baseline in the total abscess and inflammatory nodule count, with no increase from baseline in abscess or draining fistula count
HiSCR50	HiSCR defined as at least a 50% reduction from baseline in the total abscess and inflammatory nodule count, with no increase from baseline in abscess or draining fistula count
HiSCR75	HiSCR defined as at least a 75% reduction from baseline in the total abscess and inflammatory nodule count, with no increase from baseline in abscess or draining fistula count
HiSCR90	HiSCR defined as at least a 90% reduction from baseline in the total abscess and inflammatory nodule count, with no increase from baseline in abscess or draining fistula count
HiSCR100	HiSCR defined as at least a 100% reduction from baseline in the total abscess and inflammatory nodule count, with no increase from baseline in abscess or draining fistula count
HIV	human immunodeficiency virus
HRT	hormonal replacement therapy
HS	hidradenitis suppurativa
HS-PGA	Hidradenitis Suppurativa-Physician's Global Assessment
IBD	inflammatory bowel disease
ICE	Intercurrent event
ICH	International Council for Harmonisation
ICF	Informed Consent Form
IEC	Independent Ethics Committee
IHS4	International Hidradenitis Suppurativa Severity Score System
IL	interleukin
IMP	investigational medicinal product
IRB	Institutional Review Board
IXRS	Interactive Voice/Web Response System
IV	intravenous(ly)
JAK	Janus kinase
MMRM	nonlinear mixed effects model with repeated measures
NOAEL	no observed adverse effect level
NRI	non-response imputation
NRS	numeric rating scale
PASI	Psoriasis Area and Severity Index

Abbreviation	Definition
PCR	polymerase chain reaction
PGIC	Patient Global Impression of Change
PK	pharmacokinetics
PPD	purified protein derivative
PRN	as needed
QW	every week
Q2W	every other week
SAE	serious adverse event
SARS-CoV-2	severe acute respiratory syndrome coronavirus
SC	subcutaneous(ly)
SF-12v2	12-Item Short Form Survey version 2
SoA	Schedule of Activities
t _{1/2}	half-life
TEAE	treatment-emergent adverse events
Th17	IL-17-producing T-helper cells
t_{max}	time to maximum observed concentration
TNF-α	tumor necrosis factor-α
ULN	upper limit of normal
US	United States
USPI	United States prescribing information
WOCBP	women of childbearing potential

10.7. Lesion Count

Lesion counts ^a	Abscess	Non- draining fistula	Draining fistula	Non- inflammatory nodule	Inflammatory nodule	Hypertrophic scar	Longest distance (mm) between 2 relevant lesions ^b	Intervening normal appearance tissue (yes or no) ^c
Left axilla								
Right axilla								
Left sub/inframammary								
Area								
Right								
sub/inframammary area								
Intermammary area								
Left buttock								
Right buttock								
Left inguino-crural fold ^d								
Right inguino-crural fold ^d								
Perianal								
Perineal								
Upper back and neck								
Other								
Totals	1 1					-		

^a Lesion counts are to be recorded every study visit.

^b If only 1 lesion, record diameter of that single lesion.
^c Are all lesions in this area clearing and separated by normal-appearing tissues? Answer: yes or no.

^d Includes the immediate adjacent area.

10.8. Erythema Score

Example

At every visit, for each anatomic region affected by HS, the investigator will assess the overall degree of erythema using a four-point ordinal scale ranging between 0 and 3.

Region (to be assessed at every visit)	Degree of Erythema
Left axilla	
Right axilla	
Left sub/inframammary area	
Right sub/inframammary area	
Intermammary area	
Left buttock	
Right buttock	
Left inguino-crural fold	
Right inguino-crural fold	
Perianal	
Perineal	
Upper back and neck	
Other	

^{0 =} no redness; 1 = faint but discernible pink coloration; 2 = moderate red coloration; 3 = very red or bright red coloration.

10.9. Numeric Rating Scale Patient Global Assessment of Skin Pain Example

Please answer the questions below before you go to bed. Please mark an "X" in the box (\Box) which best describes the severity of your skin pain in the last 24 hours.

1. In the last 24 hours, which		in pain									ain as can ima	bad as agine
number best	1										1	
describes your skin pain at its	0	1	2	3	4	5	6	7	8	9	10	
worst due to your HS?												
2. In the last 24 hours, which		in pain									ain as can ima	bad as agine
number best	\downarrow										1	
describes your skin pain on	0	1	2	3	4	5	6	7	8	9	10	
average due to your HS?												

10.10. Daily Subject Analgesic (Pain) Use Diary – Example

Please answer the	questions below	before you g	go to bed.	Provide you	ır response ba	sed on the	past
24 hours.							

Did you take any pain medication in the past 24 hours? \square Yes \square No

If YES:

Fill in the chart with the information about the pain medication you took. If "Other" write in the name of the pain medication you took.

	Type of Pain Medication Taken (check box)	Was the Medication		Dose and Unit (example 325 mg pill)	Number of Pills Taken (example: 2 pills)
Pain Medication		□ Yes	□ No		
Ibuprofen		□ Yes	□ No		
Acetaminophen		□ Yes	□ No		
Tramadol		□ Yes	□ No		
Other pain medication:		□ Yes	□ No		
Other pain medication:		□ Yes	□ No		
Other pain medication:		□ Yes	□ No		

2.1. Overall Study Design

This is a phase 2b pivotal, multi-center, dose-finding study to evaluate the efficacy, safety, and immunogenicity of izokibep in subjects with moderate to severe Hidradenitis Suppurativa (HS).

This study consists of 2 parts, Part A and Part B as described below.

Part A: Single Arm, Open Label

Part A is a single-arm, open-label, proof-of-concept investigation to explore preliminary efficacy and safety of izokibep in adult subjects with moderate to severe HS. Part A consists of up to a 28-day screening period, a 31-week treatment period, and a follow-up period that includes 2 visits to be completed by all subjects at Week 39 and Week 45. For subjects that early terminate the follow-up visits should be completed 8-weeks (\pm 5 days) and 14 weeks (\pm 5 days) after the last dose of study drug. A minimum of 20 subjects and up to 30 subjects will be enrolled in Part A (Group 0: izokibep SC 160 mg QW from Day 1/week 0 to Week 31).

Subjects will complete study assessments according to the study visits outlined in the Schedule of Activities (SoA) in the protocol. The primary endpoint will be assessed at Week 16.

After enrollment and through the end of the study if the subject's abscess and inflammatory nodule (AN) count is $\geq 150\%$ of Day 1 AN count, antibiotic rescue medication is permitted. Subjects who qualify may initiate treatment with minocycline or doxycycline up to 100 mg BID. The dosing regimen must remain stable throughout study participation. In the case that a subject was previously intolerant or has a contraindication to both minocycline and doxycycline for the treatment of HS, the medical monitor should review to determine whether another rescue medication would be more appropriate. Rescue antibiotic therapy should be captured in the source and on the Prior and Concomitant Medications form of the CRF.

Once enrollment in Part A has finished, enrollment will begin into Part B.

Part B: Randomized, Double-blind, Dose-finding

Part B is a randomized, double-blind, placebo-controlled, parallel group, dose-finding investigation to evaluate the efficacy, safety, and immunogenicity of izokibep in subjects with moderate to severe HS. Subjects will complete up to a 28-day screening period, followed by a 16-week double-blind treatment period. At completion of the Week 16 visit procedures, subjects randomized to placebo will be switched to active treatment in a blinded manner for the Week 16 dose through Week 30 (Q2W dose group) or Week 31 (QW dose group). Subjects randomized to izokibep will remain on the same dose through Week 30 (Q2W dose

group) or Week 31 (QW dose group). After their respective treatment periods, all subjects will enter a follow-up period that includes 2 visits to be completed at Week 39 and Week 45. For subjects that early terminate the follow-up visits should be completed 8-weeks (\pm 5 days) and 14 weeks (\pm 5 days) after the last dose of study drug.

Approximately 170 subjects will be randomized into 1 of 4 groups in a 1:1:2:2 ratio as follows:

- Group 1 (n = 28-29): placebo SC QW from Day 1 (Week 0) to Week 15, then izokibep SC 160 mg QW from Week 16 to Week 31.
- Group 2 (n = 28-29): placebo SC Q2W from Day 1 (Week 0) to Week 14, then izokibep SC 160 mg Q2W from Week 16 to Week 30.
- Group 3 (n = 56-57): izokibep SC 160 mg QW from Day 1 (Week 0) to Week 31.
- Group 4 (n = 56-57): izokibep SC 160 mg Q2W from Day 1 (Week 0) to Week 30.

Randomization will be stratified by any prior biologic/Janus Kinase (JAK) inhibitor used for HS (Yes/No) and Hurley Stage (II or III).

Subjects will complete study assessments according to the study visits outlined in the SoA in the protocol. Day 1 corresponds to the first dose of study drug. All subsequent visits will be scheduled based on the Day 1 visit.

Subjects in the QW dosing groups (Group 0 [Part A], Groups 1 and 3 [Part B]) will have study visits at screening, Day 1 (Week 0), and at Weeks 1, 2, 3, 4, 8, 12, 13, 14, 15, 16, 17, 20, 24, 28, and 32 as well as at the follow-up visits.

Subjects in the Q2W dosing regimens (Groups 2 and 4 in Part B) will have study visits at screening, Day 1 (Week 0), and at Weeks 2, 4, 8, 12, 14, 16, 18, 20, 24, 28, and 32 as well as at the follow-up visits.

Subjects assigned to placebo SC QW and placebo SC Q2W will be grouped into a single placebo group for comparison to each dosing regimen of izokibep for Part B. The primary endpoint will be assessed at Week 16.

After randomization and through the end of the study if the AN count is $\geq 150\%$ of Day 1 AN count, antibiotic rescue medication will be permitted, similar to what is allowable in Part A.

2.2. Study Objectives

2.2.1. Primary Objective

The primary objective for Part A is to explore the efficacy of izokibep as measured by HiSCR75 at Week 12.

The primary objective for Part B is to demonstrate that one or both treatment regimens of izokibep is efficacious compared to placebo, as measured by HiSCR75 at Week 16.

Final, Version 3.0, 03APR2024

Page 10 of 75 ST-AD-008 version 06

2.2.2. Secondary Objectives

The secondary objectives for Part A are:

- To explore the safety and tolerability of izokibep
- To explore the immunogenicity of izokibep as measured by the presence of Anti-Drug Antibodies (ADAs)

The secondary objectives for Part B are:

- To demonstrate that one or both regimens of izokibep is efficacious, as measured by:
 - Percentage of subjects achieving HiSCR90 at Week 16;
 - Percentage of subjects achieving HiSCR100 at Week 16;
 - Percentage of subjects achieving HiSCR50 at Week 16;
 - Percentage of subjects who experience ≥ 1 disease flare through 16 weeks of treatment;
 - Percentage of subjects with baseline Hurley Stage II who achieve AN count of 0, 1, or 2 at Week 16;
 - Percentage of subjects achieving at least 3 points reduction from baseline in Numeric Rating Scale (NRS) in Patient Global Assessment of Skin Pain at its worst at Week 16 among participants with baseline NRS \ge 4.
- To assess the safety and tolerability of izokibep as measured by the incidence of Treatment-emergent Adverse Events (TEAEs), events of interest, Serious Adverse Events (SAEs), and clinically significant laboratory values and vital signs.
- To assess the immunogenicity of izokibep as measured by the presence of ADAs.

2.2.3. Exploratory Objectives

The exploratory objectives for Part B are:

- To explore if one or both regimens of izokibep is efficacious, as measured by:
 - Percentage of subjects who achieve HiSCR75 at Weeks 4, 8, 12, and 32;
 - Percentage of subjects who achieve HiSCR90 at Weeks 4, 8, 12 and 32;
 - Percentage of subjects who achieve HiSCR100 at Weeks 4, 8, 12, and 32;
 - Percentage of subjects who achieve HiSCR50 at Weeks 4, 8, 12, and 32;
 - Percentage of subjects with baseline Hurley Stage II who achieved AN count of 0, 1, or 2 at Weeks 4, 8, 12, 24, and 32;
 - NRS Patient Global Assessment of Skin Pain from baseline after 4, 8, 12, 16, 24, and 32 weeks of treatment;
 - Modified Sartorius Score after 4, 8, 12, 16, 24, and 32 weeks of treatment;
 - HS flare rates through 4 and 32 weeks of treatment;

- International Hidradenitis Suppurativa Severity Score System (IHS4), after 4, 8, 12, 16, 24, and 32 weeks of treatment;
- o Hidradenitis Suppurativa-Physician's Global Assessment (HS-PGA).
- To explore the effect of izokibep on PROs as measured by change from baseline over time in:
 - European Quality of Life-5 Dimensions (EQ-5D);
 - Dermatology Life Quality Index (DLQI);
 - Hospital Anxiety and Depression Scale (HADS).
- To evaluate the pharmacokinetics of izokibep in subjects with HS.

2.3. Sample Size and Power

In Part A, a minimum of 20 subjects and up to 30 subjects will be enrolled. With the minimum of 20 subjects enrolled if the true HiSCR response rate is 50%, an observed rate of 30% to 70% will be observed with 95% probability. Conversely, an observed response rate of 25% or lower suggests that the true rate is < 50% and an observed rate of 75% or higher suggests that the true rate is > 50%, based on limits of a two-sided 95% CI.

For Part B, power calculations were reported in protocol 21102 version 3.0, dated 26 April 2023, for the original primary endpoint of HiSCR50 and not for the updated primary endpoint of HiSCR75. Using the updated primary endpoint of HiSCR75, the comparisons of a regimen of izokibep to placebo will have approximately 55 subjects in each izokibep regimen compared to approximately 55 subjects on placebo (QW and Q2W combined). In prior studies of adalimumab in a similar patient population, a HiSCR75 response rates of 10% to 15% was observed with placebo compared with response rates of 25% to 35% with adalimumab. If true response rates with placebo and izokibep are 15% and 40%, respectively, this study will have approximately 80% power to reject the null hypothesis of equal response rates. This calculation was made in SAS® using the POWER procedure on an unstratified test of binomial proportions.

2.4. Primary Efficacy Variable

The primary efficacy variable for Part A and Part B is HiSCR75, the proportion of subjects who achieve at least a 75% reduction from baseline in the total AN count, with no increase from baseline in abscess or draining fistula count. The primary timepoint for analysis is Week 12 for Part A and Week 16 for Part B.

HiSCR50/75/90/100 is defined as meeting all three criteria below:

- (AN count at baseline AN count at current visit) / AN count at baseline \times 100% \geq 50/75/90/100%
- Abscess count at baseline \geq abscess count at the current visit
- Draining fistula count at baseline \geq draining fistula count at the current visit

where AN count is abscess count + inflammatory nodule count, and abscess count and fistula count are summed across all regions and are inclusive of all abscesses, inflammatory nodules and fistula that have previously undergone localized surgical or medical intervention and are no longer present. The baseline value for lesion count (including draining fistula count) and Hurley stage is the latest value on or before the randomization day (Day 1).

2.5. Secondary Efficacy Variables

The secondary efficacy variables for Part B are:

- HiSCR90 at Week 16
- HiSCR100 at Week 16
- HiSCR50 at Week 16
- HS flare through Week 16, where HS flare is defined as proportion meeting the following two criteria at any assessment after baseline and at or before Week 16:
 - (AN count at current visit- AN count at baseline) / AN count at baseline ×100% $\ge 25\%$
 - AN count at current visit- AN count at baseline ≥ 2
- Achieving AN count of 0, 1, or 2 at Week 16 among subjects with baseline Hurley Stage II
- NRS in Patient Global Assessment of Skin Pain at its worst at Week 16 among subjects with baseline NRS ≥ 4. NRS in Patient Global Assessment of Skin Pain at its worst is the answer from Question: In the last 24 hours, which number best describes your skin pain at its WORST due to your HS? The answer is in the range of 0 (No skin pain) to 10 (Skin pain bad as you can imagine). The skin pain score at each visit will be calculated using average of daily scores among the 7 days up to and including the day of visit, with a minimum of 4 days (consecutive or non-consecutive) with scores among the 7 days up to and including the first study drug administration day, with a minimum of 4 days with scores required. For any visit, if Patient Global Assessment of Skin Pain at its worst is available for 3 or few of the 7 days up to and including the day of visit, the pain score will be missing for analysis.

2.6. Exploratory Efficacy Variables

The exploratory efficacy variables for Part B are:

- HiSCR75 at Weeks 2, 4, 8, 12, and 32
- HiSCR90 at Weeks 2, 4, 8, 12, and 32
- HiSCR100 at Weeks 2, 4, 8, 12, and 32
- HiSCR50 at Weeks 2, 4, 8, 12 and 32

- Achieving AN count of 0, 1, or 2 at Weeks 4, 8, 12, 24, and 32 among subjects with baseline Hurley Stage II
- Change in PGA of Skin Pain (at its worst and average respectively) from baseline at Weeks 4, 8, 12, 16, 24, and 32
- Modified Sartorius Score after Weeks 4, 8, 12, 16, 24, and 32 (see Appendix for scoring method)
- HS flares through Weeks 4 and 32
- IHS4 scores at Weeks 4, 8, 12, 16, 24, and 32, where IHS4 is defined as: IHS4 score (points) = (number of inflammatory nodules × 1) + (number of abscesses × 2) + (number of draining tunnels [fistulae/sinuses] × 4)
- IHS4-55 response rates at Weeks 4, 8, 12, 16, 24 and 32, where IHS4-55 is defined as a decrease in IHS4 of 55% or more from baseline
- Change from baseline to Week 16 in HS-PGA
- Change from baseline to Week 16 in EQ-5D (see Appendix for scoring method)
- Change from baseline to Week 16 in DLQI (see Appendix for scoring method)
- Change from baseline to Week 16 in HADS, HADS-anxiety, and HADS-depression (see Appendix for scoring method)
- Trough plasma concentrations of izokibep at collected timepoints (baseline, Week 4, 8, 12, 16, 24, 32, 39, and 45)

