Exploratory biomarker sampling ^m		X				X	X					X						X		
Treatment Assignment																				
Treatment assignment/Randomization		X																		
Study drug administration and Diary	d Dosing																			
QW dosing (at site) ^{a, n}		X	X	X	X	X	X	X	X	X	X	X	X		X	X	X			
Q2W dosing (at site) ^{a, n}		X		X		X	X	X		X		X		X	X	X	X			
Dosing diary ^o																		→		

ADA = anti-drug antibody; AE = adverse event; AN = abscess and inflammatory nodule; d = day; CRF = case report form; C-SSRS = Columbia-Suicide Severity Rating Scale; DLQI = Dermatology Life Quality Index; ECG = electrocardiogram; EOS = end of study; EQ-5D = European Quality of Life 5-dimension;

ET = early termination; HADS = Hospital Anxiety and Depression Scale; HBsAg = hepatitis B surface antigen, HCV = hepatitis C virus; HS-PGIC = HS Patient Global Impression of Change; NRS = Numeric Rating Scale; PGA = Physician's Global Assessment; PK = pharmacokinetic; PPD = purified protein derivative; Q2W = every other week; QW = once weekly; SAE = serious adverse event; SF-12 = 12-Item Short Form Survey; TB = tuberculosis; WOCBP = women of childbearing potential.

- ^a Visit/dosing windows of ±3 days on either side of the scheduled visits/dosing are permitted; however, the investigator should try to keep the subjects on the original visit/dosing schedule. In case of a delayed or missed dose, the investigator should return subjects on the original visit/dosing schedule in relation to Day 1 for subsequent doses. The window of ± 3 days is relative to Day 1 and applicable for all subsequent visits/dosing. For QW dosing, the time between doses should be no less than 4 days and no more than 10 days. For Q2W dosing, the time between doses should be no less than 11 days and no more than 17 days. Study visits for QW dosing are not required at Weeks 5 to 7, 9 to 11, 18, 19, 21 to 23,25 to 27, or 29 to 31 if subject/caregiver completes study drug administration at home. Subjects randomized to Q2W arms are not required to complete visits on Weeks 1, 3, 13, 15, and 17. Study visits for Q2W dosing not required at Weeks 6, 10, 22, 26, or 30 if subject/caregiver completes study drug administration at home. See footnotes n and o below.
- ^b The follow-up period consists of 2 visits to be completed by all subjects at Week 39 and Week 45. For subjects who early terminate, the follow-up visits should be completed 8 weeks (± 5 days) and 14 weeks (± 5 days) after the last dose of study drug.

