- ^m Pharmacokinetic and ADA blood sampling will be taken prior to administration of study drug (pre-dose) on dosing days.
- ⁿ Administration of study drug should be done last after all study procedures unless indicated otherwise. Subjects will be monitored at the study site for at least one hour after study drug administrations at the following visits: for subjects enrolled to QW arms, on Day 1 and Weeks 1, 16, and 17; for subjects enrolled to Q2W arms, on Day 1 and Weeks 2, 16, and 18. After Week 4, qualified subjects may perform home dosing of study drug at weeks without study visits (see footnote a) and do not need to return to the clinical site on those weeks. Subjects may begin self-administration of study drug from Week 5 (QW dosing) or Week 6 (Q2W dosing). Subjects will be trained on study drug handling and self-administration of study drug at the study visits prior to beginning self-administration. A subject's caregiver or designee can also be trained on home dosing based on the subject's preference. Study-site staff will administer study drug at the first 2 visits. Thereafter, if home dosing is a consideration, the subject or subject's caregiver or designee must administer and demonstrate competency

for at least 2 visits prior to being allowed to dose at home. Otherwise, the subject will need to return to the site for all injections. The last dose of study drug for subjects dosed QW is Week 31 and for subjects dosed Q2W is Week 30.

[°] A dosing diary will be completed for every home dosing administration.

^p Subjects who end the study early will complete an early termination visit and complete the procedures described at the Week 32 visit within 2 weeks of the last dose of study drug.

2. Introduction

Izokibep is a potent and selective inhibitor of interleukin 17A (IL-17A) that is being developed for treatment of hidradenitis suppurativa (HS).

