To assess the safety and tolerability of izokibep as measured by the incidence of TEAEs, events of interest, SAEs, and clinically significant laboratory values and vital signs	 TEAEs, events of interest, and SAEs Laboratory values and vital signs at collected timepoints 			
To assess the immunogenicity of izokibep as measured by the presence of ADAs	• ADAs			
Exploratory				
Part B				
To explore if one or both regimens of izokibep is efficacious, as measured by:				
• Percentage of subjects who achieve HiSCR75 ¹ at Weeks 2, 4, 8, 12, and 32.	• HiSCR75 ¹ at Weeks 2, 4, 8, 12, and 32			
Percentage of subjects who achieve HiSCR90¹ at Weeks 2, 4, 8, 12, and 32	• HiSCR90 ¹ at Weeks 2, 4, 8, 12, and 32			
Percentage of subjects who achieve HiSCR100¹ at Weeks 2, 4, 8, 12, and 32	• HiSCR100 ¹ at Weeks 2, 4, 8, 12, and 32			
Percentage of subjects who achieve HiSCR50¹ at Weeks 2, 4, 8, 12, and 32	• HiSCR50 ¹ at Weeks 2, 4, 8, 12, and 32			
Percentage of subjects with baseline Hurley Stage II who achieved AN count of 0, 1, or 2 at Weeks 4, 8, 12, 24, and 32	• AN count of 0, 1, or 2 at Weeks 4, 8, 12, 24, and 32			
NRS Patient Global Assessment of Skin Pain from baseline after 4, 8, 12, 16, 24, and 32 weeks of treatment	Change in pain score from baseline at Weeks 4, 8, 12, 16, 24, and 32			
Modified Sartorius Score after 4, 8, 12, 16, 24, and 32 weeks of treatment	Modified Sartorius Score at baseline, Weeks 4, 8, 12, 16, 24, and 32			
HS flare rates through 4 and 32 weeks of treatment	HS flares through Weeks 4 and 32			

Objectives	Endpoints
• IHS4, after 4, 8, 12, 16, 24, and 32 weeks of treatment	• IHS4 scores at Weeks 4, 8, 12, 16, 24, and 32
Hidradenitis Suppurativa-Physician's Global Assessment (HS-PGA)	Change from baseline to Week 16 in HS-PGA
To explore the effect of izokibep on PROs as measured by change from baseline over time in: • EQ-5D	• Change from baseline to Week 16 in EQ-5D
• DLQI	Change from baseline to Week 16 in DLQI
• HADS	Change from baseline to Week 16 in HADS, HADS-anxiety and HADS-depression
To evaluate the pharmacokinetics of izokibep in subjects with HS	Trough plasma concentrations of izokibep at collected timepoints

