7.1. Discontinuation of Study Drug

In rare instances, it may be necessary for a subject to permanently discontinue study drug. The reason for the permanent discontinuation of study drug will be documented. If study drug is permanently discontinued, the subject will be encouraged to remain in the study to be evaluated for safety and efficacy. Subjects should continue to complete study assessments as outlined in the SoA where possible, with the exception of study drug administration. Reasons for removal from study drug include any of the following:

- subject request
- safety concern (eg, due to an AE, ineligibility determined, protocol deviation, non-compliance, pregnancy, hepatotoxicity)
- death
- lost to follow-up
- decision by sponsor (other than subject request, safety concern, lost to follow-up)
- protocol-specified reasons:
 - o A subject who requires more than 2 lesion interventions within the first 16 weeks of the study must be discontinued from study drug
 - After Week 16, a subject who requires more than 2 lesion interventions within a
 4-week period or has 2 of the same interventions on the same lesion within that
 period must be discontinued from study drug

Additionally, subjects experiencing any of the following AEs must be discontinued from study drug, but continued in the study and followed until resolution of the AE:

- Hematologic AE of moderate or severe intensity (refer to Section 10.3.3 for description of intensity assessment)
- Cardiovascular AE of moderate or severe intensity

Note: Exceptions to this requirement include the following specific cardiovascular events that represent asymptomatic findings discovered as part of testing that may have been done for other reasons most likely unrelated to the drug product or the trial itself. Cardiovascular AEs that do not meet study drug discontinuation criteria include the following AEs related to asymptomatic valvular findings and asymptomatic arrythmia findings:

- o Valvular asymptomatic findings:
 - Aortic valve: Asymptomatic valvular thickening with or without mild valvular regurgitation or stenosis by imaging
 - Mitral valve disease: Asymptomatic; moderate regurgitation or stenosis by imaging

- Pulmonary valve disease: Asymptomatic; moderate regurgitation or stenosis by imaging
- Tricuspid valvular disease: Asymptomatic; moderate regurgitation or stenosis by imaging
- o Arrythmia findings of a non-urgent medical nature:

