4.4. Pharmacokinetics Analysis Set

The Pharmacokinetics analysis set for subjects in Part A and Part B will include all subjects who received at least one administration of test material (izokibep or placebo) and have at least 1 quantifiable PK concentration.

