6.8. Pharmacokinetic Assessments

Pharmacokinetic data will be summarized by treatment group and scheduled visit, including N (number of non-missing data), N BLQ (for concentrations only), arithmetic mean, standard deviation (SD), arithmetic coefficient of variation (CV%), geometric mean, geometric CV%, median, minimum, and maximum. Only trough collections are planned, so no calculations of PK parameters (maximum concentration, area under the concentration curve, etc.) will be provided.

For the calculation of summary statistics, pre-dose concentrations that are below the limit of quantification (BLQ) will be treated as zero and post-dose concentrations that are BLQ will be treated as missing.

Pharmacokinetic data may be combined with data from other studies of izokibep for modeling. If this is done, details will be described in a separate document.

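### SAP 2.6 and 6.8 call every PK sample a trough and set no time-since-dose rule, so follow-up samples are mislabelled and off-drug samples can lower the on-treatment rows

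*SAP*

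**What the plan says.** The protocol's exploratory endpoint (Section 3) is "Trough plasma concentrations of izokibep at collected timepoints", with no list of weeks. SAP 2.6 adds the list: "Trough plasma concentrations of izokibep at collected timepoints (baseline, Week 4, 8, 12, 16, 24, 32, 39, and 45". SAP 6.8 says "Pharmacokinetic data will be summarized by treatment group and scheduled visit" and gives the absence of any non-trough collection as the reason for calculating no PK parameters.

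The Schedule of Activities (Protocol 1.3) places PK draws at Weeks 0, 2, 4, 8, 12, 16, 24, 32, 39 and 45. Its footnotes fix the timing: "Pharmacokinetic and ADA blood sampling will be taken prior to administration of study drug (pre-dose) on dosing days", and "The last dose of study drug for subjects dosed QW is Week 31 and for subjects dosed Q2W is Week 30".

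Two further rules decide whose samples count. Protocol 7.1 says of subjects who permanently stop drug: "Subjects should continue to complete study assessments as outlined in the SoA where possible, with the exception of study drug administration". SAP 4.4 admits anyone who "received at least one administration of test material (izokibep or placebo) and have at least 1 quantifiable PK concentration". SAP 5.1.4 analyses all data by nominal visit. None of these texts asks when the subject was last dosed.

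**The concern.** A trough is the concentration at the end of a dosing interval. It describes a regimen only if the previous dose was given on schedule. Two features of the plan depart from that.

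First, the label covers samples that cannot be troughs: one before treatment and two in follow-up.

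Second, a subject who stopped drug at Week 6 and still attends Week 16 contributes to the Week 16 trough row, as does a subject who missed the preceding dose. Such values are always low, so the effect runs one way. The geometric mean, which SAP 6.8 reports, is especially sensitive to a few very low values.

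This is a dose-finding study, and the by-visit concentration tables are the only PK summary the SAP commits to. If more subjects stopped drug in one regimen than in the other, part of that difference would show up in the tables as a difference in exposure.

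The Week 2 omission is smaller: the SAP 2.6 list does not match the Schedule of Activities.

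**Working it through.** **Inputs.** All are from the protocol unless stated.
- Predicted steady state for 160 mg QW (4.2, Table 2): AUC 5850 h·µg/mL, average 34.8 µg/mL, Cmin 27.2 µg/mL.
- Half-life (2.2.3.4): single-dose SC geometric mean 278 h, individual range 199 to 464 h; after repeated SC dosing, 279 h. I use 278 h = 11.58 days. These come from earlier studies, so applying them to HS is an assumption.
- Last dose: Week 31 (QW), Week 30 (Q2W).

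**Reproducing the plan's figure.** Average = AUC / interval = 5850 / 168 h = 34.8 µg/mL, as Table 2 states.

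**What each sample is.**
- Week 0: before the first dose.
- Weeks 2, 4, 8, 12, 16, 24: pre-dose at dosing visits in both schedules, so troughs for a subject receiving izokibep on schedule.
- Week 32: 32 − 31 = 1 week after the last QW dose and 32 − 30 = 2 weeks after the last Q2W dose. That is one dosing interval in each case, so a trough.
- Week 39: 8 weeks (QW) or 9 weeks (Q2W) after the last dose. Week 45: 14 or 15 weeks. Both are washout.

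So 6 of the 9 samples listed in SAP 2.6, and 7 of the 10 in the Schedule of Activities, are troughs. (SAP 5.1.3 describes Week 32 as four weeks after the last dose. That disagrees with the dosing schedule in both documents and needs reconciling; I have used the schedule.)

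**Level remaining in follow-up**, relative to the Week 32 trough, = 2^(−t / 11.58), t in days.
- Week 39, t = 49: 5.3%, or about 1.4 µg/mL from 27.2. Range 1.7% to 17.3% for half-lives of 199 to 464 h.
- Week 45, t = 91: 0.43%, or about 0.12 µg/mL. Range 0.05% to 3.8%.

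**One missed QW dose** (14 days since dosing, 7 days past the trough): 27.2 × 2^(−7 / 11.58) = 17.9 µg/mL, or 66% of the trough.

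**Off-drug subjects in the Week 16 QW row (illustration).** Let a share d of samples come from subjects whose last dose was uniform over Days 14 to 98. Time past the trough, measured from Day 112, is then uniform over 7 to 91 days.
- Mean fraction remaining = (11.58 / ln 2) / 84 × (2^(−7/11.58) − 2^(−91/11.58)) = 0.199 × (0.658 − 0.004) = 0.13.
- Fall in the arithmetic mean = d × (1 − 0.13).
- Mean time past the trough is 49 days, so geometric ratio = 2^(−49d / 11.58) = 2^(−4.23d).

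Results:
- d = 5%: arithmetic −4%, geometric −14%.
- d = 10%: −9%, −25%.
- d = 20%: −17%, −44%.

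The model starts every stopper from the steady-state trough. Early stoppers would be below it, so on that count the falls are slightly understated.

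**The case against.** A reader might infer that the reported troughs do not describe the regimens. The documents do not support that. SAP 6.8 reports by visit, so Weeks 39 and 45 sit in their own rows and cannot alter an on-treatment value; the Schedule of Activities heads those columns as follow-up. Weeks 4 to 32 are genuine troughs for subjects still dosing.

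A reader might also infer that the Week 2 data are lost. They are not: Protocol 9.3.4 covers all planned collections and SAP 6.8 covers scheduled visits. Week 2 is the only sample after a single Q2W dose, but it is not the only accumulation sample. By 1 − 2^(−t / 11.58), Weeks 2 and 4 reach about 57% and 81% of steady state.

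Nor does any text plan a comparison with the 27.2 µg/mL Cmin or a PK test of QW against Q2W.

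The size is open to challenge too. The 5% to 20% share is assumed, while Protocol 7.1 presents permanent discontinuation as rare. Only QW is modelled, so a distortion between regimens is not quantified. SAP 6.8 also reports the median, which is more robust: with an assumed between-subject CV of 33% (Protocol 2.2.3.4 gives 29.4% to 36.0% for AUC) and all off-drug values below the on-drug median, it falls by about 2%, 4% and 10%. The geometric figures assume that late samples are quantifiable, whereas SAP 5.2.4 sets post-dose BLQ values to missing and no quantification limit is given. The table shells, not public, may contain a flag, and optional modelling could account for time since dose.

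All of this limits the size and importance of the point. It does not supply the missing criterion or make Weeks 39 and 45 troughs.

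**Conclusion.** The point holds as a low-cost improvement to an exploratory, descriptive endpoint. Three things are established from the text: the trough label is wrong for baseline and Weeks 39 and 45; SAP 4.4, 5.1.4 and 6.8 together let samples taken off drug or after a missed dose into the on-treatment rows; and the SAP 2.6 list is inconsistent with the Schedule of Activities at Week 2.

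The direction of the second effect is certain: downward, and stronger in the geometric mean. Its size is not known. The 4% to 17% and 14% to 44% figures depend on the assumed off-drug share, the uniform stopping times, the half-life carried over from other populations, and quantifiable late samples. If permanent discontinuation is as uncommon as Protocol 7.1 suggests, the effect will lie at or below the lower end.

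**What to change.** In SAP 6.8:
- Summarise as trough only pre-dose samples whose time since the previous izokibep dose lies within the protocol's dosing interval. For QW the protocol says "For QW dosing, the time between doses should be no less than 4 days and no more than 10 days"; the Q2W limits are 11 to 17 days.
- Treat Week 32 separately. Those limits govern the time between doses, and no dose is given at Week 32. With ±3 days on both the last dose and the visit, a compliant sample can fall 7 ± 6 = 1 to 13 days (QW) or 14 ± 6 = 8 to 20 days (Q2W) after dosing. Use these ranges so that compliant samples are kept, and show time since dose alongside.
- Flag and list all other samples, and keep the all-observed summary by visit next to the trough table.
- Label Weeks 39 and 45 as follow-up concentrations and baseline as pre-treatment.

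In SAP 2.6, add Week 2.

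The cost is SAP wording and one derived flag. Dose dates (Protocol 6.4) and the actual date and time of each PK sample (Protocol 8.4) are already recorded. The downside is slightly fewer samples per visit in the trough table; because the all-observed summary stays, no information is lost.
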